6.2.2 Assessment of Adverse Events

Investigators will assess the occurrence of AEs and SAEs at all subject evaluation timepoints during the study. All AEs and SAEs whether volunteered by the subject, discovered by study personnel during questioning, or detected through physical examination, or other means, will be recorded in the subject's medical record and on the AE eCRF.

Disease progression itself is not considered an AE; however, signs and symptoms of disease progression may be recorded as AEs or SAEs. For additional details regarding disease progression and AEs, see [Section 6.1.1](#).

Each recorded AE or SAE will be described by its diagnostic term, duration (e.g., start and end dates), severity, regulatory seriousness criteria, if applicable, suspected

relationship to the study drug (see following guidance), and any actions taken. The causality of AEs to the study drug will be assessed by means of the question: 'Is there a reasonable possibility that the event may have been caused by the study drug?' per FDA guidance on safety reporting requirements ([FDA Guidance for Industry and Investigators: Safety Reporting Requirements for INDs and BA/BE Studies \(December 2012\)](#)).

See [Appendix 6](#) for more detail on assessing causality.

6.2.3 Second Primary Malignancies

AEs for malignant tumors reported during a study should generally be assessed as SAEs. If no other seriousness criteria apply, the "Important Medical Event" criterion should be used. In certain situations, however, medical judgment on an individual event basis should be applied to clarify that the malignant tumor event should be assessed and reported as a nonserious AE. For example, if the tumor is included as medical history and progression occurs during the study but the progression does not change treatment and/or prognosis of the malignant tumor, the AE may not fulfill the attributes for being assessed as serious, although reporting of the progression of the malignant tumor as an AE is valid and should occur. Also, some types of malignant tumors, which do not spread remotely after a routine treatment that does not require hospitalization, may be assessed as nonserious; examples in adults include Stage 1 basal cell carcinoma and Stage 1A1 cervical cancer removed via cone biopsy.

The above instruction applies only when the malignant tumor event in question is a new malignant tumor (i.e., it is not the tumor for which entry into the study is a criterion and that is being treated by the investigational product under study and is not the development of new or progression of existing metastasis to the tumor under study). Malignant tumors that—as part of normal, if rare, progression—undergo transformation (e.g., Richter's transformation of B-cell chronic lymphocytic leukemia into diffuse large B-cell lymphoma) should not be considered a new malignant tumor.

6.2.4 Pregnancy

The investigator should report all pregnancies of subjects within 24 hours using the Pregnancy Report Form. This form should be faxed or emailed to Acerta Pharma Drug Safety. Any pregnancy-associated SAE must be reported to Acerta Pharma, according to the usual timelines and directions for SAE reporting ([Section 6.2.5](#)).

Any uncomplicated pregnancy that occurs with the subject during this study will be reported. All pregnancies that are identified during or after this study, wherein the estimated date of conception is determined to have occurred from the time of consent to 90 days after the last dose of study medication will be reported, followed to conclusion, and the outcome reported.

A pregnancy itself is not regarded as an AE unless there is suspicion that the investigational product under study may have interfered with the effectiveness of a contraceptive medication. Likewise, elective abortions without complications are not considered AEs. Any SAEs associated with pregnancy (e.g., congenital abnormalities/birth defects/spontaneous miscarriage or any other serious events) must additionally be reported as such using the SAE report form.

Subjects should be instructed to immediately notify the investigator of any pregnancies. Any female subjects receiving study drug who become pregnant must immediately discontinue study drug. The investigator should counsel the subject, discussing any risks of continuing the pregnancy and any possible effects on the fetus.

Upon completion of the pregnancy, additional information on the mother, pregnancy, and baby will be collected and sent to ^{PPD} [REDACTED]

6.2.5 Expedited Reporting Requirements for Serious Adverse Events

All SAEs must be reported within 24 hours of discovery. Initial SAE reports and follow-up information will be reported using the protocol-specific electronic data capturing (EDC) system, according to the instructions provided in the investigator site file. If electronic SAE reporting is not available, paper SAE/Product Complaint forms must be emailed or faxed to Acerta Pharma Drug Safety, or designee. Email/fax is only to be used if the EDC is unavailable. Acerta Pharma may request follow-up and other additional information from the investigator (e.g., hospital admission/discharge notes and laboratory results).

Whenever possible, AEs/SAEs should be reported by diagnosis term not as a constellation of symptoms. Death due to disease progression should be recorded on the appropriate form in the EDC system. If the primary cause of death is disease progression, the death due to disease progression should not be reported as an SAE. If the primary cause of death is something other than disease progression, then the death should be reported as an SAE with the primary cause of death as the event AE term, as

death is typically the outcome of the event, not the event itself. The primary cause of death on the autopsy report should be the term reported. Autopsy and postmortem reports must be forwarded to Acerta Pharma Drug Safety, or designee, as outlined above.

If study drug is discontinued because of an SAE, this information must be included in the SAE report.

An SAE may qualify for mandatory expedited reporting to regulatory authorities if the SAE is attributable to the investigational product (or if a causality assessment is not provided for the SAE, in which case a default of “related” may be used for expedited reporting purposes) and is not listed in the current Investigator Brochure (i.e., an unexpected event). In this case, Acerta Pharma Drug Safety/Designee will forward a formal notification describing the suspected unexpected serious adverse reaction (SUSAR) to all investigators. Each investigator must then notify his or her IRB/IEC of the SUSAR.

Drug Safety Contact Information	
Fax:	PPD [redacted] (United States) or PPD [redacted] (for outside the United States)
Email:	PPD [redacted]

6.2.6 Type and Duration of Follow-up of Subjects after Adverse Events

All AEs and SAEs that are encountered during the protocol-specified AE reporting period should be followed to resolution, or until the investigator assesses the subject as stable, or the subject is lost to follow-up or withdraws consent.

7.0 STUDY ADMINISTRATION AND INVESTIGATOR OBLIGATIONS

Acerta Pharma retains the right to terminate the study and remove all study materials from a study site at any time. Specific circumstances that may precipitate such termination are:

- Unsatisfactory subject enrollment with regard to quality or quantity
- Significant or numerous deviations from study protocol requirements, such as failures to perform required evaluations on subjects and maintain adequate study records
- Inaccurate, incomplete and/or late data recording on a recurrent basis
- The incidence and/or severity of AEs in this or other studies indicating a potential health hazard caused by the study treatment

7.1 INSTITUTIONAL REVIEW BOARD AND INDEPENDENT ETHICS COMMITTEE

The investigator will submit this protocol, the informed consent, Investigator Brochure, and any other relevant supporting information (e.g., all advertising materials) to the appropriate IRB/IEC for review and approval before study initiation. A signed protocol approval page; a letter confirming IRB/IEC approval of the protocol and informed consent; and a statement that the IRB/IEC is organized and operates according to GCP guidelines and the applicable laws and regulations; **must** be forwarded to Acerta Pharma **before** screening subjects for the study. Additionally, sites must forward a signed Form FDA 1572 (Statement of Investigator) to Acerta Pharma before screening subjects for study enrollment. Amendments to the protocol must also be approved by the IRB/IEC and local regulatory agency, as appropriate, before the implementation of changes in this study.

7.2 INFORMED CONSENT AND PROTECTED SUBJECT HEALTH INFORMATION AUTHORIZATION

A copy of the IRB/IEC-approved informed consent must be forwarded to Acerta Pharma for regulatory purposes. The investigator, or designee (designee must be listed on the Study Personnel Responsibility/Signature Log, see [Section 7.11](#)), **must** explain to each subject the purpose and nature of the study, the study procedures, the possible adverse effects, and all other elements of consent as defined in § 21 Code of Federal Regulations (CFR) Part 50, and other applicable national and local regulations governing informed consent form. Each subject must provide a signed and dated informed consent before enrollment into this study. If allowed by the protocol, a legal representative may sign the informed consent form for a subject incapable of giving consent. Signed consent forms must remain in each subject's study file and be available for verification by study monitors at any time.

In accordance to individual local and national patient privacy regulations, the investigator or designee **must** explain to each subject that for the evaluation of study results, the subject's protected health information obtained during the study may be shared with Acerta Pharma and its designees, regulatory agencies, and IRBs/IECs. As the study sponsor, Acerta Pharma will not use the subject's protected health information or disclose it to a third party without applicable subject authorization. It is the investigator's or designee's responsibility to obtain written permission to use protected health information from each subject, or if appropriate, the subject's legal guardian. If a subject

or subject's legal guardian withdraws permission to use protected health information, it is the investigator's responsibility to obtain the withdrawal request in writing from the subject or subject's legal guardian **and** to ensure that no further data will be collected from the subject. Any data collected on the subject before withdrawal will be used in the analysis of study results.

7.3 SUBJECT SCREENING LOG

The investigator **must** keep a record that lists **all** subjects considered for enrollment (including those who did not undergo screening) in the study. For those subjects subsequently excluded from enrollment, record the reason(s) for exclusion.

7.4 CASE REPORT FORMS

Authorized study site personnel (see [Section 7.11](#)) will complete eCRFs designed for this study according to the completion guidelines that will be provided within the clinical database. The investigator will ensure that the eCRFs are accurate, complete, legible, and completed promptly. Refer to [Section 7.7](#) for record retention requirements.

7.5 STUDY MONITORING REQUIREMENTS

Representatives of Acerta Pharma or its designee will monitor this study until completion. The purpose of monitoring is to ensure compliance with the protocol and the quality and integrity of the data. This study is also subject to reviews or audits.

Every effort will be made to maintain the anonymity and confidentiality of all subjects during this clinical study. However, because of the experimental nature of this treatment, the investigator agrees to allow the IRB/IEC, representatives of Acerta Pharma, its designated agents, and authorized employees of the appropriate regulatory agencies to inspect the facilities used in this study and, for purposes of verification, allow direct access to the hospital or clinic records of all subjects enrolled into this study. This includes providing by fax, email, or regular mail de-identified copies of radiology, pathology, and/or laboratory results when requested by the sponsor. A statement to this effect will be included in the informed consent and permission form authorizing the use of protected health information.

7.6 INVESTIGATIONAL STUDY DRUG ACCOUNTABILITY

Acalabrutinib capsules must be kept in a locked limited access cabinet or space. The study drug must not be used outside the context of the protocol.

Study drug accountability records must be maintained and readily available for inspection by representatives of Acerta Pharma and are open to inspections by regulatory authorities at any time.

All study supplies and associated documentation will be regularly reviewed and verified by the monitor.

7.7 RECORD RETENTION

The investigator and other appropriate study staff are responsible for maintaining all documentation relevant to the study. Mandatory documentation includes copies of study protocols and amendments, each Form FDA 1572, IRB/IEC approval letters, signed ICFs, drug accountability records, SAE information transmitted to Acerta Pharma, subject files (source documentation) that substantiate entries in eCRFs, all relevant correspondence and other documents pertaining to the conduct of the study.

An investigator shall retain records for a period of at least 2 years after the date the last marketing application is approved for the drug for the indication for which it is being investigated; or, if no application is to be filed or if the application is not approved for such indication, until 2 years after the investigation is discontinued and regulatory authorities have been notified. The investigator must notify Acerta Pharma and obtain written approval from Acerta Pharma before destroying any clinical study records at any time. Acerta Pharma will inform the investigator of the date that study records may be destroyed or returned to Acerta Pharma.

Acerta Pharma must be notified in advance of, and Acerta Pharma must provide express written approval of, any change in the maintenance of the foregoing documents if the investigator wishes to move study records to another location or assign responsibility for record retention to another party. If the investigator cannot guarantee the archiving requirements set forth herein at his or her study site for all such documents, special arrangements must be made between the investigator and Acerta Pharma to store such documents in sealed containers away from the study site so that they can be returned sealed to the investigator for audit purposes.

7.8 PROTOCOL AMENDMENTS

Acerta Pharma will initiate any change to the protocol in a protocol amendment document. The amendment will be submitted to the IRB/IEC together with, if applicable, a revised model ICF. If the change in any way increases the risk to the subject or

changes the scope of the study, then written documentation of IRB/IEC approval must be received by Acerta Pharma before the amendment may take effect. Additionally under this circumstance, information on the increased risk and/or change in scope must be provided to subjects already actively participating in the study, and they must read, understand, and sign any revised ICF confirming willingness to remain in the trial.

7.9 PUBLICATION OF STUDY RESULTS

Authorship, in general, will follow the recommendations of the International Committee of Medical Journal Editors ([ICJME 2014](#)).

7.10 CLINICAL TRIAL INSURANCE

Clinical trial insurance has been undertaken according to the laws of the countries where the study will be conducted. An insurance certificate will be made available to the participating sites at the time of study initiation.

7.11 GENERAL INVESTIGATOR RESPONSIBILITIES

The principal investigator must ensure that:

1. He or she will conduct or supervise the study.
2. His or her staff and all persons who assist in the conduct of the study clearly understand their responsibilities and have their names included in the Study Personnel Responsibility/Signature Log.
3. The study is conducted according to the protocol and all applicable regulations.
4. The protection of each subject's rights and welfare is maintained.
5. Signed and dated informed consent and, when applicable, permission to use protected health information are obtained from each subject before conducting nonstandard of care study procedures. If a subject or subject's legal guardian withdraws permission to use protected health information, the investigator will obtain a written request from the subject or subject's legal guardian and will ensure that no further data be collected from the subject.
6. The consent process is conducted in compliance with all applicable regulations and privacy acts.
7. The IRB/IEC complies with applicable regulations and conducts initial and ongoing reviews and approvals of the study.
8. Any amendment to the protocol is submitted promptly to the IRB/IEC.
9. Any significant protocol deviations are reported to Acerta Pharma and the IRB/IEC according to the guidelines at each study site.
10. CRF pages are completed promptly.
11. All IND Safety Reports/ SUSAR Reports are submitted promptly to the IRB/IEC.

12. All SAEs are reported to Acerta Pharma Drug Safety/Designee within 24 hours of knowledge via the clinical database and to the IRB/IEC per their requirements.

Appendix 1. Schedule of Assessments

Cycles	Screening ^e	Treatment Phase ^a												TT Visit	SFU Visit ^b	Post-Treatment Disease Follow-Up ^c	LTFU ^d
		Cycle 1				Cycle 2				Cycles 3-4		Cycles 5+					
Study Days		1	8	15	22	1	8	15	22	1	15	1		+7 days after last dose	+30 days after last dose	Q12W	Q12W
Study Window	-21 days	±3 days				±3 days				±3 days		±3 days		+7 days	+7 days	±10 days	±10 days
Informed consent	x																
Confirm eligibility	x																
Medical history	x																
PE ^f /Vital signs ^g /Weight	x	x	x	x	x	x	x	x	x	x	x	x	x	x	x		
ECOG status	x	x	x	x	x	x	x	x	x	x	x	x	x				
ECG ^h	x																
Lab assessments:																	
Urine or serum pregnancy test ⁱ	x	x ^j												x	x		
Hematology ^k	x	x	x	x	x	x	x	x	x	x		x	x	x	x		
Serum chemistry ^l	x	x	x	x	x	x		x		x		x	x	x	x		
Coagulation panel ^m	x	x	x	x	x	x		x		x		x	x				
Urinalysis ⁿ	x	x	x	x	x	x		x		x		x	x				
CCI																	
EIAEDs plasma concentration monitoring ^o		x	x	x	x	x				x		x					EIAEDs plasma concentration monitoring ^o
Hepatitis serology ^f	x																
HBV PCR ^s						x				x		Q3M				Q3M	Q3M
CCI																	
Acalabrutinib 200 mg BID or 400 mg QD ^v		Continuous Dosing															
MRI (CNS) ^w	x									x		Every 8 weeks starting with Cycle 6				x	

Cycles	Screening ^e	Treatment Phase ^a										TT Visit	SFU Visit ^b	Post-Treatment Disease Follow-Up ^c	LTFU ^d	
		Cycle 1				Cycle 2				Cycles 3-4						Cycles 5+
Study Days		1	8	15	22	1	8	15	22	1	15	1	+7 days after last dose	+30 days after last dose	Q12W	Q12W
Study Window	-21 days	±3 days				±3 days				±3 days		±3 days	+7 days	±10 days	±10 days	
CCI																
Concomitant medications ^z																
Corticosteroids	x	x	x	x	x	x	x	x	x	x	x	x	x	x		
EIAEDs																
Adverse events		x	x	x	x	x	x	x	x	x	x	x	x	x	x	
Survival													x	x		x

anti-HBc=hepatitis B core antibody; anti-HBs=hepatitis B surface antibody; BID=twice per day; CR=complete remission; DFU=disease follow-up; ECOG=Eastern Cooperative Oncology Group; EIAEDs=enzyme-inducing anti-epileptic drugs; CCI HBsAg=hepatitis B surface antigen; HBV=hepatitis B virus; HCV=hepatitis C virus; LTFU=long-term follow-up; MRI=magnetic resonance imaging; CCI PCR=polymerase chain reaction; CCI PE=physical examination; Q12W=every 12 weeks; Q3M=every 3 months; SAC=Scientific Advisory Committee; TT=treatment termination.

Footnotes for ACE-ST-209 Schedule of Study Activities:

- Any subjects who are tolerating study drug and have not progressed at the end of trial, defined as 52 weeks after the last subject is enrolled to the study, may continue to receive their study treatment after discussion with the medical monitor. They will continue to have scheduled visits as outlined for Cycles 5+ on the schedule of assessments.
- A 30-day (+7 days) safety follow-up visit is required when subjects discontinue study drug. After the end of the protocol-defined adverse event reporting period (see Section 6.2.1), only serious adverse events considered related to study drug(s) or study procedures are required to be collected.
- Each subject should be followed until disease progression or the start of alternative anticancer therapy. If neither of these has occurred at the time of the 30-day SFU visit, DFU visits should occur approximately every 3 months (12 weeks) from date of last dose until disease progression or next anticancer treatment. During this period, subjects will be followed via MRIs.
- Once subjects progress or start use of alternative anticancer therapy—for all subjects who have not withdrawn consent—they will be contacted approximately every 3 months (12 weeks) from date of last dose by clinic visit or telephone, to assess survival and the use of alternative anticancer therapy until death or lost to follow-up.
- An MRI must be performed within 21 days before the administration of study drug; all other screening tests should be performed within 21 days before the first administration of study drug, unless otherwise indicated.

- f. The screening physical examination will include, at a minimum, the general appearance of the subject, height (screening only) and weight, and examination of the skin, eyes, ears, nose, throat, lungs, heart, abdomen, extremities, musculoskeletal system, lymphatic system, and nervous system. Symptom-directed physical examinations, including tumor assessments by palpation, are done thereafter.
- g. Vital signs (blood pressure, pulse, and temperature) will be assessed after the subject has rested in the sitting position.
- h. An ECG will be performed during screening. Subjects should be in supine position and resting for ≥ 10 minutes before the ECG.
- i. Women of childbearing potential only.
- j. This urine or serum pregnancy test is to be performed on Cycle 1 Day 1 (-3 days).
- k. Hematology includes complete blood count with differential including, but not limited to white blood cell count, hemoglobin, hematocrit, platelet count, ANC, and ALC. Cycle 1 Day 1 hematology does not need to be repeated if screening hematology was done within 10 days.
- l. Serum chemistry: albumin, alkaline phosphatase, ALT, AST, bicarbonate, BUN, calcium, chloride, creatinine, glucose, LDH, magnesium, phosphate/phosphorus, potassium, sodium, total bilirubin, total protein, and uric acid. Cycle 1 Day 1 serum chemistry does not need to be repeated if screening serum chemistry was within 10 days. If an unscheduled ECG is done at any time, then an electrolyte panel (i.e., calcium, magnesium, and potassium) must be done to coincide with the ECG testing.
- m. PT and aPTT.
- n. Urinalysis: pH, ketones, specific gravity, bilirubin, protein, blood, and glucose.

CCI

- q. For subjects who are receiving the EIAEDs carbamazepine or phenytoin, who are either enrolled in the Phase 1b portion or approved by the medical monitor to participate in this study: blood samples for therapeutic drug monitoring for carbamazepine and/or phenytoin levels will be drawn predose and 1 hour postdose on Cycle 1 Day 1, anytime during the visit on Cycle 1 Day 8, predose and 1 hour postdose on Cycle 1 Day 15 and Cycle 1 Day 22, and then monthly thereafter, and should be repeated after any dose change, until sufficient data are available to discern that time-dependent inhibition of CYP3A is or is not a concern. The predose sample can be taken up to 30 minutes before dosing. The window for other timepoints is ± 5 minutes. Therapeutic drug monitoring will be performed locally. Refer to the protocol for more detailed information. Note: Under Amendment 2 of the protocol, no additional subjects on EIAEDs will be enrolled.
- r. Hepatitis serology must include HBsAg, anti-HBs, anti-HBc, and HCV antibody. In addition, any subjects testing positive for any hepatitis serology, must have PCR testing (see exclusion criterion #23).
- s. Subjects who are anti-HBc positive (or have a known history of HBV infection) should have a quantitative PCR test for HBV DNA performed during screening and every 3 months thereafter. Regular monitoring (every 3 months) should continue until 12 months after last dose of acalabrutinib. Any subject with a rising viral load (above lower limit of detection) should discontinue acalabrutinib and have antiviral therapy instituted and a consultation with a physician with expertise in managing hepatitis B.

CCI

- v. Under Amendment 2 of the protocol, the SAC observed that the response and disease-control rate observed in the 200-mg BID cohort were numerically higher than in the 400-mg QD cohort. Therefore, the 400-mg QD cohort was discontinued.
- w. An MRI of the CNS must be performed at screening, on Cycle 3 Day 1, Cycle 4 Day 1 (4 weeks after Cycle 3 Day 1 scan to evaluate for response stability), then on Day 1 of every other cycle (every 8 weeks) thereafter (e.g., Cycle 6 Day 1, Cycle 8 Day 1); if symptomatic, then MRIs may be performed more frequently at investigator discretion.

CCI

- z. Concomitant medications of interest that will be collected throughout the study include corticosteroids and EIAEDs. Note: Under Amendment 2 of the protocol, no additional subjects on EIAEDs will be enrolled.

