5.0 STATISTICAL METHODS OF ANALYSIS

5.1 GENERAL CONSIDERATIONS

Descriptive statistics will be used to summarize baseline demographic and disease characteristics, study drug administration, efficacy, and safety outcomes, PK parameters, and PD markers. Descriptive summaries of discrete data will present the sample size and the incidence as a frequency and as a percentage. Descriptive summaries of continuous data will present the sample size, group mean, standard deviation, median, and range. CIs will be included as appropriate. There are 2 timepoints for analyses: (1) the interim analysis will occur approximately 8 weeks (2 cycles) after the 12th subject has been enrolled in each cohort in the Phase 1b portion of the study, and (2) the final analysis will occur 24 weeks after the last subject is enrolled to the study.

Note: Under Amendment 2 of the protocol, the 2nd interim analysis will be performed approximately when 7 additional non-EIAED subjects complete 16 weeks (4 cycles) of treatment.

Statistical Basis for the Sample Size

The sample size for this study included subjects enrolled in Phase 1b and Phase 2 treated with the same dose regimen. An ORR observed in standard of care for second-line therapies (CCNU) ranged around 5 to 10%. While bevacizumab (Avastin) demonstrated an ORR >20%, considerable toxicities were reported. To reject the null hypothesis of ORR ≤5% in favor of an alternative hypothesis that the ORR is ≥20%, 43 subjects will preserve approximately 88% power to detect the difference at a 0.025 significance level by a 1-sided exact test.

Note: Under Amendment 2 of the protocol, the sample size for this study will include subjects enrolled in Phase 1b and Phase 2 and treated with the same dose regimen. Subjects enrolled in Phase 1b but treated with a different dose regimen not chosen for investigation in Phase 2, will not be included in these sample size calculations.

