5.4.4 Analysis of Efficacy Parameters

Response Rate

ORR is defined as the proportion of subjects who achieve a CR or partial response (remission) (see [Section 4.2](#)). ORR will be calculated, and the corresponding 2-sided exact 95% CI will be derived.

Duration of Response

For subjects who achieve objective response, DOR is defined as the time from the first tumor assessment showing response to the time of confirmed disease progression or death due to any cause, whichever occurs first. Subjects who are still alive and free from progression at the time of data cutoff date, are lost to follow-up, have discontinued from the study, or have initiated other non-protocol antitumor therapy (NPT) will be

censored at the last evaluable tumor assessment. A Kaplan-Meier (K-M) curve will be presented for DOR and K-M median will be calculated with 2-sided 95% CI.

Progression-Free Survival

PFS is defined as the time from first dose to documented disease progression, or death from any cause, whichever occurs first. Subjects who are still alive and free from progression at the time of data cutoff date, are lost to follow-up, have discontinued from the study, or have initiated NPT will have their PFS time censored at last evaluable assessment (or, if there is no post-baseline tumor assessment, at the time of first dose). A K-M curve will be presented, and K-M estimates as well as exact 2-sided 95% CIs will be calculated for event time quartiles, and event-free rates at the protocol-specified disease assessment times.

6-month and [CCI] Progression-Free Survival Rates

PFS-6 rate is defined as the K-M estimate of subjects alive and without documented disease progression at 6 months. In this study, 1 month is defined as 30.4375 days. The K-M method will be used to estimate the PFS-6 rate and corresponding 95% CIs.

[CCI]

Overall Survival

Overall survival (OS) is defined as the time from first dose to death from any cause. Subjects who are still alive at the time of data cutoff date, are lost to follow-up, or have discontinued from the study will have their OS time censored at the last date known to be alive on or before the data cutoff date. The analysis of OS will be conducted, where applicable, using the same analysis method described for PFS.

The SAP will describe analyses of all other exploratory endpoints.

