#### **6-month Progression-free Survival (PFS-6) Rates and 4-month Progression-free Survival (PFS-4) Rates**

PFS-6 rate is defined as the K-M estimate of subjects alive and without documented disease progression at 6 months. The K-M method will be used to estimate the PFS-6 rate and corresponding exact 2-sided 95% CIs. The same method applies to the PFS-4 rate.

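### The 4- and 6-month PFS landmarks fall between scheduled MRIs, so Kaplan-Meier PFS-4 and PFS-6 are biased upward for progression found only on a scheduled scan

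*Protocol*

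**What the plan says.** **Scan times.** Protocol Appendix 1, footnote w, calls for a CNS MRI at screening, at Cycle 3 Day 1, at "Cycle 4 Day 1 (4 weeks after Cycle 3 Day 1 scan to evaluate for response stability"), and "then on Day 1 of every other cycle (every 8 weeks) thereafter (e.g., Cycle 6 Day 1, Cycle 8 Day 1"). The same sentence adds that "if symptomatic, then MRIs may be performed more frequently at investigator discretion". On-treatment visits have a window of ±3 days.

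**Landmarks.** Protocol 5.4.4 states: "In this study, 1 month is defined as 30.4375 days". It also says: "PFS is defined as the time from first dose to documented disease progression, or death from any cause, whichever occurs first".

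**Estimator.** SAP 10.7.3 states: "PFS-6 rate is defined as the K-M estimate of subjects alive and without documented disease progression at 6 months". It adds: "The same method applies to the PFS-4 rate".

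**Event dates.** SAP Appendix 12.3 dates progression at the visit that documents it, scheduled or unscheduled. It dates a death between adequate assessments on the day of death. It censors a subject who stops treatment for undocumented progression at the last adequate assessment.

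**Other rates.** Protocol 5.4.4 also plans Kaplan-Meier event-free rates at the scheduled assessments. SAP 10.7.3 lists only curves, quantiles, PFS-6 and PFS-4.

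**The concern.** A Kaplan-Meier curve can fall only on dates when an event is recorded. If a landmark lies well after one scheduled scan and shortly before the next, tumour growth that starts in between and causes no symptoms is recorded after the landmark. Those subjects count as progression-free at the landmark although they have already progressed. The error runs in one direction, and the planned confidence intervals do not reflect it.

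PFS-6 is a named secondary objective in a study with no comparator, and PFS-4 is a further listed efficacy endpoint. What is at stake is how the two percentages are understood: part of each may reflect where the scans fall rather than disease control.

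**Working it through.** **The plan's own figures.** The documents give no numerical assumption for PFS-6 or PFS-4, so there is none to reproduce. The design figure for ORR does reproduce: with 43 subjects, 5% against 20%, rejecting at 6 or more responses gives a one-sided alpha of 0.0194 and power of 88.5%. This point does not affect it.

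**Step 1: the calendar.** Protocol 5.1 speaks of "7 additional non-EIAED subjects complete 16 weeks (4 cycles) of treatment", so a cycle is 16 × 7 / 4 = 28 days. Day 1 of cycle c falls (c − 1) × 28 days after first dose.

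| Scheduled scan | Days after first dose | With ±3-day window |
|---|---|---|
| Cycle 3 Day 1 | 56 (week 8) | 53 to 59 |
| Cycle 4 Day 1 | 84 (week 12) | 81 to 87 |
| Cycle 6 Day 1 | 140 (week 20) | 137 to 143 |
| Cycle 8 Day 1 | 196 (week 28) | 193 to 199 |

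The landmarks are 4 × 30.4375 = 121.75 days and 6 × 30.4375 = 182.6 days.

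- PFS-6: the last nominal scan is 182.6 − 140 = about 43 days earlier. The next can come no sooner than 193 − 182.6 = about 10 days later.
- PFS-4: the last nominal scan is 121.75 − 84 = about 38 days earlier. The next can come no sooner than 137 − 121.75 = about 15 days later.

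The window does not close either gap. The SAP's study-day convention, which counts first dose as day 1, shifts times by one day and changes nothing.

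**Step 2: a ceiling on the bias.** Two assumptions are mine and not in the documents: PFS is exponential with median m months, and progression is detected only at scheduled scans held on their nominal days. Then S(t) = 2^(−t / (30.4375 m)). The curve read at day 182.6 equals S(140), and the curve read at day 121.75 equals S(84). For m = 2, S(140) = 2^(−140/60.875) = 20.3% against a true S(182.6) = 2^(−3) = 12.5%.

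| Median (months) | PFS-6 read | PFS-6 true | Excess (points) | PFS-4 read | PFS-4 true | Excess (points) |
|---|---|---|---|---|---|---|
| 1.5 | 11.9% | 6.2% | 5.7 | 27.9% | 15.7% | 12.2 |
| 2 | 20.3% | 12.5% | 7.8 | 38.4% | 25.0% | 13.4 |
| 3 | 34.6% | 25.0% | 9.6 | 52.9% | 39.7% | 13.2 |
| 4 | 45.1% | 35.4% | 9.7 | 62.0% | 50.0% | 12.0 |
| 6 | 58.8% | 50.0% | 8.8 | 72.7% | 63.0% | 9.7 |

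**Step 3: allow for events caught on time.** If a share f of events is recorded at its true time, through death, clinical progression or a symptom-triggered scan, the excess is multiplied by (1 − f). The documents do not give f. At f = 0.5 the excess is about 3 to 5 points for PFS-6 and 5 to 7 for PFS-4. At f = 0.75 it is about 1 to 2 and 2 to 3 points.

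**Step 4: test the obvious remedy.** Suppose progressions found at Cycle 6 Day 1 and Cycle 8 Day 1 were counted as events by 4 and 6 months. At a 2-month median PFS-4 would read S(140) = 20.3% against a true 25.0%, and PFS-6 would read S(196) = 10.7% against a true 12.5%. The bias changes sign.

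**Step 5: compare with sampling error.** In the 15-subject cohort, 7.8 points is 0.078 × 15 = about 1.2 subjects. Ignoring censoring, 3 of 15 has an exact 95% interval of about 4% to 48%.

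**The case against.** The strongest reply is that a reader might infer that PFS-6 simply reports week-20 status and PFS-4 week-12 status. The documents do not support that. SAP Appendix 12.3 counts deaths and progressions at unscheduled visits on their own dates, and footnote w permits extra MRIs for symptoms. Protocol Table 4-1 treats clear clinical deterioration as progression. Appendix 1 schedules an examination and ECOG status on Day 1 of Cycles 5 and 7, about 10 and 15 days before the two landmarks. The RANO paper in Appendix 2 dates progression back to when the question was first raised. All of this stands, and it makes the table above a ceiling.

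It does not remove the bias. Extra MRIs are optional, and growth without symptoms waits for the schedule. Back-dating helps only where doubt had already been recorded. SAP 10.7.3 asks for objective progression, and undocumented progression is censored rather than counted. Off treatment, Protocol 4.4.1 leaves MRI timing to the investigator.

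A second reply is that the endpoint is defined by documented progression, which Kaplan-Meier on documentation dates estimates as defined. That is fair. The bias is relative to true progression time, and the SAP should say so.

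A reader might also infer that the result would mislead against a PFS-6 benchmark. The documents give none, and SAP section 5 tests no hypothesis. An outside comparison would be distorted mainly if the other study scanned on a different schedule.

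**Conclusion.** The point holds in limited form. Both landmarks fall between scheduled MRIs whatever the visit window. Progression seen only on a scheduled scan and arising after day 140 (PFS-6) or day 84 (PFS-4) is dated after the landmark, so both rates lean upward relative to true progression time.

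The direction follows from the documents; the size does not. The ceilings of about 6 to 10 and 10 to 13 points rest on the exponential model, the assumed medians and detection at scheduled scans alone. The real excess depends on the share of events caught between scans.

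The consequence is modest. Phase 2 was not started, the analysis describes cohorts of 15 and 9, and sampling error exceeds even the ceiling. No decision in the plan depends on either rate. The bias is nonetheless systematic and cheap to make visible, and SAP 10.7.3 leaves out the protocol's own scan-time rates that would do so.

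**What to change.** In SAP 10.7.3, restore the Kaplan-Meier event-free rates at the scheduled assessments from Protocol 5.4.4. Read them just after the Cycle 6 Day 1 and Cycle 8 Day 1 windows close (140 + 3 = day 143 and 196 + 3 = day 199). Label them week-20 and week-28 PFS. Show them beside the nominal PFS-4 and PFS-6, with a note giving the scan dates and the direction of the bias.

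Do not present them as 4- and 6-month rates, because step 4 shows that this biases downward. An interval-censored (Turnbull) estimate is suitable only as a sensitivity analysis. It does not determine how events are spread within a gap such as day 140 to day 196, so the within-interval assumption must be stated.

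The cost is a few lines of SAP text and one extra, somewhat lower displayed rate per landmark. No scans or new data are needed. If the SAP is already final, its introduction allows the change to be documented in the clinical study report.
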